# **10 Safety monitoring, reporting and committees**

## **10.1 Definition of adverse events and reporting requirements**

### **10.1.1 Expected adverse events**

For the study-mandated procedures/requirements listed below, only the signs and symptoms listed under each procedure will be considered outside normal range and will be recorded as an

adverse event (AE) (see [Section 10.1.2](#) for definition of AE). For all other study-mandated procedures/requirements not listed in this section, all AEs will be recorded.

Skin Prick Test: The following events related to SPT will be considered AEs if they occur within 48 hours of the SPT:

- Prolonged (>24 hours) pruritus at the SPT site
- Induration/swelling at the SPT site larger than 10 mm in diameter and lasting more than 24 hours
- Allergic or anaphylactic reaction that requires the use of rescue medications

DBPCFC: The following events related to an DBPCFC will be considered AEs:

- Severe dose-limiting symptoms as defined by

As moderate dose-limiting symptoms are the usual threshold at which an DBPCFC will be considered positive to a food (allergen), almost every positive DBPCFC would be recorded as an AE, which will dilute the true incidence of AEs for this trial. To avoid artificially increasing the AE incidence from DBPCFCs, only severe dose-limiting symptoms as defined by [Section 16.4.6](#) will be considered AEs. However, all reactions that occur during a DBPCFC will be captured in the appropriate eCRF.

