#### 10.1.4 SAE reporting

To ensure participant safety, every SAE, regardless of causality, occurring after the participant has provided informed consent and until 30 days after the last study visit must be reported to Novartis safety immediately, without undue delay, but under no circumstances later than within 24 hours of obtaining knowledge of the events (Note: if more stringent, local regulations regarding reporting timelines prevail). Any SAEs experienced after the 30 day period should only be reported to Novartis Safety if the investigator suspects a causal relationship to study treatment, unless otherwise specified in local regulations. Any SAEs reported up to the participant's last visit will be reported in the eCRF. SAEs beyond that date will only be recorded in the Novartis Safety database. Detailed instructions regarding the submission process and requirements are to be found in the investigator folder provided to each site.

Information about all SAEs is collected and recorded on the electronic Serious Adverse Event Report Form (eSAE) (with paper backup if required); all applicable sections of the form must be completed in order to provide a clinically thorough report.

1. Screen Failures (e.g. a participant who is screened but is not treated or randomized): SAEs occurring after the participant has provided informed consent until the time the participant is deemed a Screen Failure must be reported to Novartis with 24 hours of learning of its occurrence.
2. Randomized OR Treated Participants: SAEs collected between time participant signs ICF until 30 days after the participant has discontinued from study treatment.

All follow-up information for the SAE including information on complications, progression of the initial SAE and recurrent episodes must be reported as follow-up to the original episode immediately, without undue delay, but under no circumstances later than within 24 hours of the Investigator receiving the follow-up information (Note: if more stringent, local regulations regarding reporting timelines prevail) of the investigator receiving the follow-up information. An SAE occurring at a different time interval or otherwise considered completely unrelated to a previously reported one must be reported separately as a new event.

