If the SAE is not previously documented in the Investigator's Brochure (new occurrence) and is thought to be related to the investigational treatment, a Chief Medical Office and participant Safety (CMO&PS) Department associate may urgently require further information from the investigator for Health Authority reporting. Novartis may need to issue an Investigator Notification (IN) to inform all investigators involved in any study with the same investigational treatment that this SAE has been reported.

Suspected Unexpected Serious Adverse Reactions (SUSARs) will be collected and reported to the competent authorities and relevant ethics committees in accordance with EU Guidance 2011/C 172/01 or as per national regulatory requirements in participating countries.

Any SAEs experienced after the 30 day period following the last study visit should only be reported to Novartis Safety if the investigator suspects a causal relationship to study treatment, unless otherwise specified by local law/regulations.

Hypersensitivity reactions during DBPCFC are expected. These events will not be reported as AE/SAE. Please refer to [Section 16.4](#) for the assessment, reporting and management of serious hypersensitivity reactions observed during the DBPCFC and the post-DBPCFC observation period.

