## 16.4.6 Evaluation parameters of the DBPCFC

Objective symptoms exhibited by participants should be evaluated through physical examination. Complaints arising from the participant without observable changes will be classified as subjective.

The DBPCFC will be **positive** with the occurrence of any dose-limiting symptom(s). Dose-limiting symptoms indicate a true allergic reaction occurring during administration of a single dose that should preclude the administration of any further doses. Investigators must adhere to [Table 16-6](#) (CoFAR grading scale) for definition of dose-limiting symptoms ([Chinthrajah et al 2022](#)). According to the CoFAR grading scale, symptoms are classified as mild, moderate or severe. Investigators must not deviate from the severity score when deciding to continue or discontinue the DBPCFC in order to ensure the precision of the procedure and to preserve the safety of the participants.

The DBPCFC is positive when the occurrence of any dose limiting symptom(s) is/are detected as below:

- Any moderate and severe symptom(s) as defined in [Table 16-6](#) (CoFAR grading scale)
- Any symptom(s) that require administration of any rescue medication (e.g., SABA, epinephrine or other)
- A combination of mild symptoms during a single dose as defined in [Table 16-6](#), at the discretion of the investigator

Once any of the dose limiting symptom(s) described above are observed, the next dose of DBPCFC must not be administered.

All findings that the investigator classifies as reactions to the DBPCFC should be recorded in source documentation and on a designated eCRF. These events should not be reported on the Adverse Event eCRF unless they constitute an SAE according to the investigator's judgement.

The details and start time of any treatment and/or medication provided to treat DBPCFC-related allergic reactions should be recorded on the respective eCRF. The DBPCFC will be considered **negative** if a participant does not exhibit dose-limiting symptom(s) by the end of the challenge.

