#### Adverse event reporting

If the participant experiences an allergic reaction associated with the DBPCFC (immediate, delayed or late-onset) that meets the criteria for a serious adverse event in the investigator's judgment, it should be captured on the designated CFR and reported as described in [Section 10.1.3 SAE Reporting](#).

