### 2.7.1 Adverse events (AEs)

All AEs summarized will be displayed by treatment group and overall. All AEs listings will be presented by treatment arm and participant.

All events that the investigator classifies as reactions associated to the DBPCFC or SPT must be captured on the designated eCRF and will not be reported on the AE eCRF. These events will be reported separately and not included in reporting of treatment-emergent AEs (events started after the first dose of study medication or events present prior to start of treatment but increased in severity based on preferred term).

The number (and percentage) of participants with treatment emergent AEs will be summarized in the following ways:

1. by treatment, primary system organ class and preferred term
2. by treatment, primary system organ class, preferred term and maximum severity
3. by treatment, Standardized MedDRA Query (SMQ) and preferred term

Separate summaries will be provided for study medication related AEs, death, serious adverse events (SAEs), and other significant AEs leading to discontinuation. In case of sparse events in any of these categories occur, only a listing will be provided if deemed adequate.

A participant with multiple AEs within a primary system organ class is only counted once towards the total of the primary system organ class.

For the legal requirements of clinicaltrials.gov, two required tables on treatment-emergent AEs which are not SAEs with an incidence greater than a certain threshold based on the final database and on treatment-emergent SAEs and SAEs suspected to be related to study treatment will be provided by system organ class and PT on the safety set population.

If for a same patient, several consecutive AEs (irrespective of study treatment causality, seriousness and severity) occurred with the same SOC and PT:

- a. a single occurrence will be counted if there is  $\leq 1$  day gap between the end date of the preceding AE and the start date of the consecutive AE
- b. more than one occurrence will be counted if there is  $> 1$  day gap between the end date of the preceding AE and the start date of the consecutive AE

For occurrence, the presence of at least one SAE / SAE suspected to be related to study treatment / non SAE has to be checked in a block e.g., among AE's in a  $\leq 1$  day gap block, if at least one SAE is occurring, then one occurrence is calculated for that SAE.

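### The protocol and SAP give conflicting rules on whether severe or serious food-challenge reactions are recorded and counted as AEs or SAEs

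*Protocol*

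**What the plan says.** Six places in the current text govern how a reaction to the challenge is recorded or counted.

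- **Protocol 10.1.1** introduces its list with "The following events related to an DBPCFC will be considered AEs" and names severe dose-limiting symptoms. It gives the reason for the cut-off: "To avoid artificially increasing the AE incidence from DBPCFCs, only severe dose-limiting symptoms as defined by" Section 16.4.6 are to count. All challenge reactions also go on their own eCRF.
- **Protocol 10.1.4** opens by requiring immediate reporting, within 24 hours at most, of "every SAE, regardless of causality, occurring after the participant has provided informed consent". It ends with "Hypersensitivity reactions during DBPCFC are expected. These events will not be reported as AE/SAE". The next sentence refers the reader to Section 16.4 "for the assessment, reporting and management of serious hypersensitivity reactions observed during the DBPCFC and the post-DBPCFC observation period".
- **Protocol 12.5.2.1** sends every event the investigator classifies as a challenge reaction to the designated eCRF, bars it from the AE eCRF, and leaves it out of treatment-emergent AE (TEAE) reporting.
- **Protocol 16.4.6** says: "These events should not be reported on the Adverse Event eCRF unless they constitute an SAE according to the investigator's judgement".
- **Protocol 16.4.7** (adverse event reporting) covers immediate, delayed and late-onset reactions. For one "that meets the criteria for a serious adverse event in the investigator's judgment, it should be captured on the designated CFR and reported", it cites Section 10.1.3 as the SAE reporting section.
- **SAP 2.7.1** repeats 12.5.2.1: "These events will be reported separately and not included in reporting of treatment-emergent AEs". It separately plans an SAE summary and registry tables of treatment-emergent SAEs.

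**The concern.** A site cannot comply with all of these rules, and a programmer cannot tell from the SAP which events belong in which table. Treatment-emergent AEs are part of the stated safety endpoint. The SAP on-treatment period runs from Day 1 to 28 days after the end of treatment, so the Day 26 and Day 28 challenges fall inside it. If some sites follow 10.1.1 and enter a severe reaction as an AE while others follow 12.5.2.1 and do not, part of any difference in severe-AE counts between arms reflects site practice. The arms are small enough for one or two events to show.

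For serious reactions the stake is whether the SAE tables are complete, and whether a reader who stops at the 10.1.4 exclusion would report the event at all. SAE status also enters the treatment discontinuation rule in 9.1.1 and, if the event is judged drug-related, the enrolment hold in 9.3.

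**Working it through.** The plan states no figure on this point, so the check is a comparison of the rules followed by a sense of scale.

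**Rules side by side**

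| Section | Severe, not serious | Serious |
|---|---|---|
| Protocol 10.1.1 | AE | AE if severe; seriousness not addressed |
| Protocol 10.1.4, general rule | No rule | Report as SAE |
| Protocol 10.1.4, challenge sentence | Not AE or SAE | Not AE or SAE as worded; next sentence refers to 16.4 |
| Protocol 12.5.2.1 | Off AE eCRF, out of TEAEs | Same, no exception |
| Protocol 16.4.6 | Off AE eCRF | On AE eCRF |
| Protocol 16.4.7 | Silent | Designated form plus SAE reporting, citing 10.1.3 |
| SAP 2.7.1 | As 12.5.2.1 | As 12.5.2.1; separate SAE summary planned |

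*Severe, not serious.* 10.1.1 stands against the 10.1.4 challenge sentence, 12.5.2.1, 16.4.6 and SAP 2.7.1. One might try to reconcile them by calling such a reaction an AE that is simply held on another form. That fails: 10.1.1 sets the cut-off at severe to stop moderate reactions from inflating AE incidence, which makes sense only if severe ones do count towards it. 10.1.1 also relies on 16.4.6 for the definition, and 16.4.6 then gives the opposite recording rule.

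*Serious.* The 10.1.4 general rule, 16.4.6 and 16.4.7 all lead to reporting. Against them stand the wording of the 10.1.4 challenge sentence and the absence of any SAE exception in 12.5.2.1 and SAP 2.7.1. The cross-reference in 16.4.7 is wrong: 10.1.3 defines SAEs, and reporting is in 10.1.4, which is also where the exclusion sits. The matching text for the skin prick test in Appendix 5 cites 10.1.4 correctly.

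*Analysis.* SAP 2.7.1 assumes that challenge reactions never reach the AE eCRF. 10.1.1 and 16.4.6 each put some there. The SAP does not say whether those are removed from or kept in the TEAE tables, nor whether challenge SAEs appear in the SAE summaries.

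*Scope.* The TEAE conflict concerns the end-of-treatment challenges, since the screening challenges precede dosing. The SAE conflict covers screening too, because SAE reporting starts at consent.

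**Scale**

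Inputs from Protocol 12.8: 72 participants, allocation 2:2:2:1:1 (8 parts), about 10% discontinuation.

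- Arm sizes: 72 × 2/8 = 18 for each one-month remibrutinib arm; 72 × 1/8 = 9 for the one-week arm and for placebo.
- One participant reclassified, with everyone randomised also dosed: 100/18 = 5.6 points; 100/9 = 11.1 points.
- Reaching the end-of-treatment challenge: 72 × 0.9 = 64.8, about 65. The protocol's per-arm completer ranges give 3 × 14 + 2 × 7 = 56 to 3 × 16 + 2 × 8 = 64, so 65 is slightly generous.
- Participants classified differently under 10.1.1 and 12.5.2.1 (64.8 × rate), with the severe-reaction rate **assumed** because the documents give none:

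| Assumed rate | Participants affected |
|---|---|
| 2% | 1.3 |
| 5% | 3.2 |
| 10% | 6.5 |
| 20% | 13.0 |

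**The case against.** The best defence is that the parts work together better than single sentences suggest, and much of it stands.

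- **Lost expedited reporting.** A reader might infer that a life-threatening reaction on blinded drug would go unreported under 10.1.4. The section as a whole does not support that. It opens with the duty to report every SAE, its sentence after the exclusion refers serious reactions to 16.4, and 16.4 requires reporting. SAEs also have their own report form, so keeping an event off the AE eCRF does not itself block the report. The risk comes only from reading the exclusion literally and in isolation.
- **Compromised discontinuation and hold rules.** A reader might infer this too, but the links are conditional. 9.1.1 exempts anaphylaxis unrelated to study drug that does not need admission for 24 hours or more, and its hypersensitivity item is limited to events unrelated to the challenge. 9.3 counts drug-related SAEs and hypersensitivity unrelated to the challenge. Dosing ends on Day 28 in any case. One conditional route remains: if a part 2A reaction were an SAE outside the exemption, treatment would stop, 9.1.1 would cancel part 2B, and SAP 1.2.1 requires both parts for the primary population.
- **Uninterpretable challenge safety.** Not so. Every reaction goes on a designated eCRF, and SAP 2.6.1 already summarises maximum symptom severity by challenge dose up to 3000 mg. It does not cover seriousness or reactions after discharge.
- **Deliberate exclusion.** Leaving challenge reactions out of TEAEs is a legitimate analysis choice, worded alike in both documents, and neither expressly removes challenge SAEs from the SAE summary.

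None of this resolves the severe, non-serious case or supplies the missing SAP rule.

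**Conclusion.** The conflict is real and lies in operative text. It is clearest for severe, non-serious reactions, where 10.1.1 cannot be reconciled with the other sections. For serious reactions the likely intent is to report, but the exception is unstated in 10.1.4, 12.5.2.1 and SAP 2.7.1, and 16.4.7 points to the wrong section.

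The consequence is that AE and SAE tables may differ by site or by programmer. The per-participant shifts of 5.6 and 11.1 points assume exact allocation and that all randomised participants are dosed. The number affected, roughly 1 to 13, rests wholly on the assumed rates of 2% to 20%; it shows scale and is not an estimate. No SAE rate can be derived from the documents. This is an inconsistency that should be corrected, not a flaw in the design.

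**What to change.** Reconcile Protocol 10.1.1, 10.1.4, 12.5.2.1, 16.4.6 and 16.4.7 and SAP 2.7.1 to one rule that separates severe from serious:

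1. Limit the 10.1.4 exclusion to non-serious challenge reactions.
2. Correct the cross-reference in 16.4.7 to the SAE reporting section.
3. Name one form for severe, non-serious reactions and use it in every section. The sponsor should choose and state whether these count as AEs.
4. State in SAP 2.7.1 that challenge reactions meeting SAE criteria are counted in the SAE tables, and how any challenge event found on the AE eCRF is handled in the TEAE tables.

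No new severity table is needed, since SAP 2.6.1 largely covers it. The cost is a protocol clarification with the matching SAP text, a site memo, and reconciliation of events already recorded. Design, sample size and the efficacy model are unchanged.

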#### **10.1.5 Pregnancy reporting**

If a female trial participant becomes pregnant, the study treatment should be stopped, and pregnancy consent form should be presented to the trial participant. The participant must be given adequate time to read, review and sign the pregnancy consent form. This consent form is necessary to allow the investigator to collect and report information regarding the pregnancy. To ensure participant safety, each pregnancy occurring after signing the informed consent must be reported to Novartis within 24 hours of learning of its occurrence. The pregnancy should be followed up to determine outcome, including spontaneous or voluntary termination, details of the birth, and the presence or absence of any birth defects, congenital abnormalities, or maternal and/or newborn complications.

Pregnancy should be recorded and reported by the investigator to the Novartis Chief Medical Office and Subject Safety (CMO&PS). Pregnancy follow-up should be recorded on the same form and should include an assessment of the possible relationship of the study treatment to any pregnancy outcome. The follow-up should be for up to 12 months following the birth of the baby. Any SAE experienced during pregnancy must also be reported.

After consent is provided, the pregnancy reporting will occur up to one year after the estimated date of delivery.

#### **10.1.6 Reporting of study treatment errors including misuse/abuse**

Medication errors are unintentional errors in the prescribing, dispensing, administration or monitoring of a medicine while under the control of a healthcare professional, participant or consumer (Committee for Medicinal Products for Human Use (CHMP) Qualification Opinion of MCP-Mod as an efficient statistical methodology for model-based design and analysis of Phase II dose finding studies under model uncertainty, [CHMP 2014](#)).

Misuse refers to situations where the medicinal product is intentionally and inappropriately used not in accordance with the protocol.

Abuse corresponds to the persistent or sporadic, intentional excessive use of a medicinal product, which is accompanied by harmful physical or psychological effects.

Study treatment errors and uses outside of what is foreseen in the protocol will be recorded on the appropriate eCRF irrespective of whether or not associated with an AE/SAE and reported to Safety only if associated with an SAE. Misuse or abuse will be collected and reported in the safety database irrespective of it being associated with an AE/SAE within 24 hours of Investigator's awareness.

**Table 10-1 Guidance for capturing the study treatment errors including misuse/abuse**

Treatment error type	Document in Dosing eCRF (Yes/No)	Document in AE eCRF	Complete SAE form
Unintentional study treatment error	Yes	Only if associated with an AE	Only if associated with an SAE
Misuse/Abuse	Yes	Yes	Yes, even if not associated with an SAE

For more information on AE and SAE definition and reporting requirements, please see the respective sections.

## 10.2 Additional Safety Monitoring

### 10.2.1 Liver safety monitoring

To ensure participant safety and enhance reliability in determining the hepatotoxic potential of an investigational drug, a standardized process for identification, monitoring and evaluation of liver events has to be followed.

Please refer to [Section 16.2](#) for complete definitions of liver laboratory triggers.

Once a participant is exposed to study treatment, every liver event defined in [Table 16-1](#) should be followed up by the investigator or designated personnel at the trial site, as summarized below. Additional details on actions required in case of liver events are outlined in [Table 16-2](#) and [Table 16-3](#). Repeat liver chemistry tests (i.e. ALT, AST, TBL, PT/INR, ALP and G-GT) to confirm elevation.

- These liver chemistry repeats will be performed using the central laboratory. If results will not be available from the central laboratory, then the repeats can also be performed at a local laboratory to monitor the safety of the participant. If a liver event is subsequently reported, any local liver chemistry tests previously conducted that are associated with this event should have results recorded on the appropriate eCRF.
- If the initial elevation is confirmed, close observation of the participant will be initiated, including consideration of treatment interruption if deemed appropriate.
- Discontinuation of the investigational drug (refer to the Discontinuation of study treatment section), if appropriate
- Hospitalization of the participant if appropriate
- Causality assessment of the liver event
- Thorough follow-up of the liver event should include
  - These investigations can include based on investigator's discretion: serology tests, imaging and pathology assessments, hepatologist's consultancy; obtaining more detailed history of symptoms and prior or concurrent diseases, history of concomitant drug use, exclusion of underlying liver disease, imaging such as abdominal US, CT or MRI, as appropriate, obtaining a history of exposure to environmental chemical agents.

All follow-up information and procedures performed must be recorded as appropriate in the eCRF.

